ACE, Resilience, and Substance Use Disorder: Maternal and Baby Outcomes in the First Year of Life

Investigator: [name], MD

Co-Investigators: [name], [name], [name], MS, PhD, MBA, [name], MA

2/19/2020

1. Objective/ Purpose

The purpose of this study is to understand the maternal factors that contribute to the health of an infant born to a mother with substance use disorder (SUD). We will evaluate whether or not the outcomes of maternal and baby health can be identified early through maternal screening tools, including the Adverse Childhood Experience (ACE) questionnaire and the 7Cs Resiliency Tool.

2. Hypothesis

Mothers with SUDs that have higher maternal ACE scores will have children with poor outcomes, including difficulty reaching developmental milestones, poorer adherence to vaccination schedule guidelines, and more frequent ER visits in the first year of life. However, high maternal resilience scores may counter the high ACE scores and allow for improvement of poor health outcomes in these populations.

3. Background

Adverse Childhood Experiences (ACEs) are traumatic or life-threatening events that occurred to an individual during the ages 0-17 and are measured with the ACE Score questionnaire. These experiences include being a victim of physical and sexual abuse, neglect, and exposure to household dysfunction such as parental substance abuse or incarceration¹. Multiple studies have shown that the number of ACEs an individual experiences correlates with his or her risk in developing chronic health issues such as diabetes, asthma, and hypertension later in life²⁻⁴. In addition, ACEs correlate with a higher risk of engaging in risky behaviors such as substance use⁵.

A recent survey conducted by the Substance Abuse and Mental Health Services Administration (SAMHSA) showed that 5.4% of pregnant mothers had used illicit drugs including marijuana, opioids, and cocaine in the past month⁶. Moreover, ACE scores of pregnant women have been linked to poor coping mechanisms such as illicit drug use during pregnancy⁷. These scores also impact prenatal,

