perinatal, and post-natal health⁸. For example, babies who were exposed to opioids in utero had significant associations with poorer health outcomes and delays in developmental stages⁹. Another study concluded that mothers suffering from substance use disorder engage in poor parenting practices such as “limited or absent parental monitoring and lower levels of parental involvement.”¹⁰ Currently, many medical practices are using ACE scores as a general screening tool to help identify health risks and provide individualized care and family support¹¹. Recent studies show that identifying positive childhood experiences is important when evaluating the impact of ACEs. Protective factors, such as resilience, can offset the negative health impacts of trauma^{12,13}. Described as good outcomes in the face of a threat to wellbeing¹³, resilience can be quantified by using a questionnaire called the 7Cs tool¹⁴. The 7Cs tool, which examines an individual’s competence, confidence, character, connection, contribution, coping and control, is a valid method to measure resilience. Currently, the 7Cs tool is internally validated for adolescents that have experienced trauma, and it has shown a correlation between better outcomes with a higher resilience score despite having higher ACE scores. Overall, there is limited information regarding ways to identify and determine the health impact of maternal resilience. More research is necessary to understand how ACEs and resilience affect postpartum outcomes in mothers with SUD and their child.

Significance of the Research

Currently, little research has been conducted to study the relationship between ACEs and maternal resilience and the health outcomes of mothers with SUDs and their newborn baby. Understanding factors that show a strong correlation with maternal and fetal health outcomes would allow health care providers to identify risks earlier, offer prenatal interventional care, and provide tailored resources for mothers and their infant.

4. Study Design

This is a prospective observational study that will require the initial administration of both the ACEs questionnaire and 7Cs resilience tool, followed by one year of chart reviews and/or phone calls to follow-up with patients regarding the identified outcome measures.

5. Proposed research Plan

A. Subjects

Number of subjects: 100

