Inclusion criteria: Pregnant mother past her 1st trimester of pregnancy who is being seen at Cooper University Hospital Addiction Medicine clinic or Labor and Delivery or Maternal Fetal Medicine Unit. The subject is diagnosed with substance use disorder.

Exclusion criteria: Mothers under the age of 18.

Recruiting Methods: Subjects will be recruited through the Addiction Medicine clinic at Cooper Hospital. Staff at the clinic will ask any pregnant mothers, past their first trimester, if they are interested in participating in this study. Interested participants will be contacted by study co-investigators to learn more about the study. If all inclusion criteria is met, the pregnant woman will be invited to participate in the study.

Informed Consent Process: Prospective subjects will meet with either of the study co-investigators named earlier in the proposal. Additionally, prospective subjects may meet with the clinical psychologist on the study, [name]. All subjects will be given a copy of the informed consent to read along with the study co-investigators. Potential subjects will be invited to a private room away from distractions and will be allowed adequate time to ask questions and read the consent forms.

Vulnerable Subjects: This study will include vulnerable subjects, namely pregnant women and their child.

Compensation to Subjects: No financial or other compensation will be offered to the subjects in exchange for participating in this study.

Treatment for Research-Related Injuries: No research-related injuries are anticipated in relation to participating in this study. If any research-related injuries are sustained during the course of this study, the subject may reach out to the research investigator or co-investigators to determine the appropriate course of action. While conducting ACEs and resilience interviews, re-traumatization will be a concern which would be handled by the current resources available through the Addiction Medicine clinic and Cooper Hospital.

B. Research Methods and Procedures

General description of methods and procedures: After consenting to participate in this study, pregnant mothers will be provided a modified survey based off of the Adverse Childhood Experiences (ACE)

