questionnaire and 7C Resilience Tool. After giving birth, patient charts will be monitored for maternal commitment to treatment, child custody status, the number of times the child was admitted to the emergency room, adherence to recommended pediatric vaccination schedules, and infant developmental milestones. These measurements will be taken over the course of 1 year after child birth.

Summary of visit procedures: Pregnant mothers will meet with any of the co-investigators prenatally to complete the ACE questionnaire and 7C Resilience Tool. After the initial intake, outcome measures will be collected via chart review or verbally through phone call with the mother. Data will be collected at birth, 2 months, 4 months, 6 months, and 1 year after birth.

Procedures just for research purposes: The ACEs questionnaire and 7C Resilience Tool are not included in standard prenatal care and are solely being administered for research purposes. If the subjects were not enrolled in this study, the only difference in care would be the absence of either screening tool being administered prenatally.

How participation differs from standard of care/ study duration: As an observational study, participating subjects will be provided the appropriate standard-of-care.

Study Duration: Pregnant mothers will be enrolled between March 1, 2020 to August 1, 2020. All mothers will be followed for one year postpartum. The total duration of the project for the individual will be the duration of the pregnancy as well as the child's first year of life. This study will be conducted between March 1, 2020 - January 31, 2020.

Data Analysis Plan, Statistical Tests, and Sample Size Rationale

Outcome measures being followed at birth of baby, and at 2, 4, 6 and 12 months after birth:

1. Is the mother still parenting and have custody of the baby?
2. Is the mother receiving treatment for substance use disorder?
3. Has the baby reached expected developmental and health milestones after delivery?
4. How many Emergency Room visits did the baby have postnatally?
5. Does the child meet vaccination schedule as proposed by the CDC?

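### The infant milestone item merges development with health and states no age basis, so it does not isolate development and preterm infants can be scored as delayed because of birth timing

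*Combined protocol and SAP*

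**What the plan says.** Section 2 (Hypothesis) predicts that infants of mothers with higher ACE scores will have "difficulty reaching developmental milestones". This is the first infant outcome it names, and it concerns development only.

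The outcome list in Section 5.B (Data Analysis Plan) turns this into item 3: "Has the baby reached expected developmental and health milestones after delivery". The list is introduced by "Outcome measures being followed at birth of baby, and at 2, 4, 6 and 12 months after birth". On the source, Section 5.B (Summary of visit procedures) says that "outcome measures will be collected via chart review or verbally through phone call with the mother". No milestone reference, cut-off, rater or age basis is given.

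Eligibility does not depend on gestation at delivery. The only exclusion in Section 5.A is maternal age ("Exclusion criteria: Mothers under the age of 18"). Gestational age at birth, prematurity and corrected age are not mentioned anywhere. The Data Analysis paragraph plans GEE models and odds ratios with 95% confidence intervals for ACE and 7C, and names no covariates.

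On a possible link between ACE and birth timing, Section 3 (Background) says of ACE scores in pregnant women: "These scores also impact prenatal", and the sentence goes on to perinatal and post-natal health. It does not mention preterm birth.

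**The concern.** There are two separate measurement problems.

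First, the item joins two things in one yes/no. An infant who is delayed but well and an infant who is ill but developing on schedule both get a no. An odds ratio for this item cannot be read as an odds ratio for development, which is what the hypothesis is about. This follows from the wording alone.

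Second, contacts are timed from birth and nothing tells the chart reviewer or the mother which age the expected milestones refer to. If chronological age is used, a preterm infant can be scored as delayed when it is on schedule for its age from term. A paediatric chart entry may allow for prematurity when a mother answering by phone does not, so the same infant could be coded differently by source. If preterm birth is also more frequent at higher ACE, the error follows the exposure and pushes the ACE odds ratio for missed milestones above 1 with no effect on attainment for corrected age. With no gestational age on the data sheet, the analysis file would not show this.

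**Working it through.** **The plan's own figure.** Section 5.B claims more than 90% power with 100 mothers for an odds ratio of 2 per SD of ACE at a response proportion of 0.50. For one observation per mother, power = Φ(√(N·p·(1−p))·ln OR − 1.96) = Φ(√(100 × 0.25) × 0.693 − 1.96) = Φ(1.51) = 93.4%. Four visits with within-mother correlation ρ = 0.5 give an effective N of 400/(1 + 3 × 0.5) = 160 and power of 99.2%. The claim reproduces, and this point does not change it.

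**Age gap at each contact.** Corrected age in weeks = months × 30.44/7 − (40 − gestational weeks).

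| Contact | Chronological age | Born at 34 weeks | Born at 32 weeks |
|---|---|---|---|
| 2 months | 8.7 | 2.7 | 0.7 |
| 4 months | 17.4 | 11.4 | 9.4 |
| 6 months | 26.1 | 20.1 | 18.1 |
| 12 months | 52.2 | 46.2 | 44.2 |

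The gap is a constant 6 or 8 weeks, so it matters most at the early contacts. At 2 months an infant born at 32 weeks is less than one week past term-equivalent age.

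**Size of a possible artefact, high versus low ACE.** The documents give none of the rates needed, so all inputs here are assumptions:
- ACE has no effect on development at corrected age.
- 10% of term infants are scored delayed.
- A proportion q of preterm infants, 30% or 50%, are scored delayed without age correction.
- The preterm share f is 10% or 15% at low ACE and 20% or 30% at high ACE.

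Proportion scored delayed = 0.10 × (1 − f) + q × f.

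| Preterm share, low v high ACE | q = 0.3: delayed, low v high | OR | q = 0.5: delayed, low v high | OR |
|---|---|---|---|---|
| 15% v 20% | 0.13 v 0.14 | 1.09 | 0.16 v 0.18 | 1.15 |
| 10% v 20% | 0.12 v 0.14 | 1.19 | 0.14 v 0.18 | 1.35 |
| 15% v 30% | 0.13 v 0.16 | 1.27 | 0.16 v 0.22 | 1.48 |
| 10% v 30% | 0.12 v 0.16 | 1.40 | 0.14 v 0.22 | 1.73 |

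For example, the smallest is (0.14/0.86)/(0.13/0.87) = 1.09 and the largest is (0.22/0.78)/(0.14/0.86) = 1.73. If f is the same in both groups, the two proportions are equal and the odds ratio is 1.00.

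**Same question per SD of ACE, the scale of the plan's power statement.** Here ACE acts only through preterm birth. The overall preterm share is 10–30%, and milestones are missed by 10% v 30%, 15% v 50% or 15% v 90% of term v preterm infants. These are again assumptions, and the 90% is an extreme.

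| Preterm odds ratio per SD of ACE | Artefact OR per SD | Chance of a significant result (100 mothers, 4 visits, ρ 0.5–1.0) |
|---|---|---|
| 1.0 | 1.00 | 5% |
| 1.2–1.5 | 1.03–1.31 | about 5–38% |
| 2.0 | 1.12–1.56 | about 7–78% |

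A middle case has 20% preterm, 15% v 50% missed and a preterm odds ratio of 1.5 per SD. Overall 0.8 × 0.15 + 0.2 × 0.50 = 22% miss the milestone and the artefact OR is 1.14. The chance of a significant result is 8% at ρ = 1.0 and 10% at ρ = 0.5.

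**The case against.** **The documents do not say that chronological age is used.** This stands. A reader might infer that preterm infants will be scored as delayed, but timing the contacts from birth does not settle the age against which milestones are judged. Expected milestones are undefined, and a chart entry may already be age-corrected. What remains is a risk, including inconsistency between chart and phone, not an established misclassification.

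**The link from ACE to preterm birth is inferred.** This also stands. The Background sentence is general. The other relevant statement there, "babies who were exposed to opioids in utero had significant associations with poorer health outcomes and delays in developmental stages", is about opioid exposure. It says nothing of prematurity or of an ACE gradient, and every mother in this study has a substance use disorder. Without such a link the artefact is 1.00.

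**Gestational age could be retrieved later.** Probably so, since charts are reviewed and data are collected at birth. It would be too strong to say that the study could never separate birth timing from development. But a retrieved gestational age does not repair a yes/no already given by phone on an unknown age basis.

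**Preterm birth may be a mediator.** Childhood adversity precedes the pregnancy, so gestational age may lie on the path from ACE to development, and the stated purpose is early identification of risk. This is a good argument against routine adjustment for gestational age. It does not touch the scoring rule: true delay in preterm infants at corrected age would still count, and only the part due to the birth date is removed.

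**Milestones are not named among the primary outcomes.** The Data Analysis paragraph names parenting, custody and continued treatment, and milestones fall at most under its closing etc. The general description in Section 5.B also lists developmental milestones without health. The first limits the weight of the point. The second shows that the intent was probably developmental, but the itemised outcome is still the combined one.

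**Conclusion.** The point holds as a measurement weakness. The combined yes/no does not isolate the developmental outcome in the hypothesis, and this needs no assumption. In addition, preterm infants can be scored as delayed because of birth timing, and differently by source, because no age basis is stated and gestational age is not listed.

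Whether this biases the ACE odds ratio depends on two conditions that the documents do not establish: scoring without age correction, and an association between ACE and preterm birth. If both hold, the assumed rates give a spurious high-versus-low odds ratio of about 1.09 to 1.73. If ACE and preterm birth are unrelated it is 1.00. These figures are illustrative and are not an estimate for this study. The documents do not support the stronger conclusion that an observed ACE effect on development would be due to prematurity.

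**What to change.** 1. Add gestational age at birth to the data sheet, taken from the delivery chart.
2. Name one milestone reference for both chart and phone sources. At the 2, 4, 6 and 12-month contacts, score developmental milestones against corrected age for infants born before 37 weeks.
3. Replace item 3 by two yes/no items, developmental milestones and health status, and test the milestone hypothesis on the developmental item.
4. Do not adjust the main ACE model for gestational age by default, because it may be on the path from ACE to development. State whether the target is the total association or the part not through preterm birth.

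The cost is one chart field, one extra item and one scoring rule. Somewhat fewer infants will be scored as delayed, which lowers the event count. For scale, the power formula above, with an odds ratio of 2 per SD and four visits at ρ between 1.0 and 0.5, gives 79–94% when 20% of infants miss a milestone and 55–75% when 10% do. The events given up through age correction are those that reflect birth timing, not development.

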Sample size. The key outcomes of the study will include binary measurements (parenting, custody, continued treatment, etc.) measured at 2, 4, 6 and 12 months after birth. These outcomes will be related to the pre-natal scores of the ACE and 7C survey tools. Based on a repeated measures design, a sample size of 100 will provide >90% power to detect an odds ratio of 2 or greater for each standard deviation above the mean of the ACE scale (1-10) assuming a mean of 3.7 and a standard deviation of 2.7 and a response proportion of 0.50.

Data Analysis. The checking, assessment and analysis of the data will be carried out in a blinded fashion. Demographic and clinical characteristics will be presented using means with standard deviation for continuous variables and counts with proportions for categorical variables. The statistical analysis will be carried out using “intention-to treat” and “per-protocol” approaches. The primary outcomes (parenting, custody, continued treatment, etc.) will be analyzed using generalized estimating equations (GEE) appropriate for repeated measures over time. Odds ratios with 95% confidence intervals for the relationships of ACE and 7C with the clinical outcomes will be presented.

6. Risks and benefits

- A. Potential Risks due to Study Participation: No study treatments will be included in this observational study. However, in some cases, re-traumatization is a possibility and necessary resources will be made available to the subject.
- B. Minimizing Risks: Risks to subjects will be minimized by the study design, which is observational and not anticipated to be risky towards the mother or fetus. Subjects being seen at the Addiction Medicine clinic and Labor and Delivery Ward will have normal access to treatment and follow-up visits, which follows normal standard of care at Cooper Hospital.
- C. Potential Benefits: Potential benefits of this study would be increased adherence to substance use disorder (SUD) treatment, appropriate follow-up with pediatricians per recommended vaccination schedule, and identifying risk factors during pregnancy to initiate early intervention practices. Society may benefit from this research by understanding the risks of ACEs and resilience scores of pregnant mothers suffering from SUD and how it affects the care of their newborn child. The findings of this

study may benefit the resources and management of mothers with SUD during pregnancy and postpartum.

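### ER visits are hypothesised as a frequency and collected as a count, but the only stated effect measure is an odds ratio, and the plan does not say whether each assessment counts new or cumulative visits

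*Combined protocol and SAP*

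**What the plan says.** Section 2 (Hypothesis) predicts, for infants of mothers with higher ACE scores, "more frequent ER visits in the first year of life". Section 5.B collects the matching data as a number in two places. The general description of methods lists "the number of times the child was admitted to the emergency room", and item 4 of the outcome list asks "How many Emergency Room visits did the baby have postnatally". Of the five listed outcomes this is the only one posed as a quantity; the other four are yes/no questions.

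The timing is given. The summary of visit procedures states: "Data will be collected at birth, 2 months, 4 months, 6 months, and 1 year after birth". Under Study Duration: "All mothers will be followed for one year postpartum".

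On analysis, the Sample size paragraph says: "The key outcomes of the study will include binary measurements (parenting, custody, continued treatment, etc". The Data Analysis paragraph says: "The primary outcomes (parenting, custody, continued treatment, etc.) will be analyzed using generalized estimating equations (GEE) appropriate for repeated measures over time". It then says: "Odds ratios with 95% confidence intervals for the relationships of ACE and 7C with the clinical outcomes will be presented". It names no distribution or link, count model, rate ratio or exposure term, and gives no rule for turning the ER count into a yes/no variable. ER visits are not named among the primary outcomes, but that list ends open, so their status is unclear.

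**The concern.** The analysis text serves the four yes/no outcomes and leaves the one count without a matching model or effect measure. If the odds-ratio sentence is taken to cover ER visits, the count has to be collapsed. An infant with four visits in an interval then counts the same as an infant with one, and the reported number says who had any visit, not how much more often visits occurred. The hypothesis is about the latter.

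The second gap is in data collection. A count taken at 4 months could mean visits since the 2-month contact or all visits since birth. If staff reading charts, or mothers answering by phone, interpret the question differently, later analysis may not be able to repair it.

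**Working it through.** **1. The plan's own figure.** The only stated power is above 90% for an odds ratio of 2 per SD of ACE, with N = 100 and response proportion 0.50 (Sample size paragraph). Two-sided 5% is assumed because no alpha is stated. For logistic regression on a standardised covariate at one time point:

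Power = Φ(√(N·p·(1−p))·ln OR − 1.96) = Φ(√25 × 0.693 − 1.96) = Φ(1.506) = 93.4%.

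With four repeated measures and an assumed within-subject correlation from 0.9 down to 0.3, it is 95.0% to 99.9%. The figure reproduces and is not disputed here. It applies to a binary outcome and does not carry over to an ER count.

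**2. The schedule.** Assessments at 2, 4, 6 and 12 months give intervals of 2, 2, 2 and 6 months. If running totals were entered as repeated responses, a visit in months 0–2 would enter four times and one in months 6–12 once. At a constant rate the average is (2 + 4 + 6 + 12)/12 = 2.0 entries per visit. The plan does not say this will be done; the arithmetic shows why the counting rule has to be stated.

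**3. Assumed inputs.** The documents give no ER rate, dispersion or target rate ratio. Assumed: r = 0.5, 1 or 2 visits a year; negative binomial counts with dispersion k = 0.5 or 1.0; complete follow-up. For a window of t months with mean m = r·t/12:

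P(any visit) = 1 − (1 + k·m)^(−1/k).

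At r = 1 this is 14.8% (k = 0.5) or 14.3% (k = 1.0) for a 2-month interval, and 36.0% or 33.3% for the 6-month interval.

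**4. Visits left out by an any-visit split per interval.** Share left out = 1 − [sum of P(any visit) over the four intervals]/r. For r = 1, k = 0.5: 1 − (3 × 0.148 + 0.360)/1 = 19.6%.

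| Visits/year | k = 0.5 | k = 1.0 |
|---|---|---|
| 0.5 | 11.0% | 13.8% |
| 1 | 19.6% | 23.8% |
| 2 | 32.4% | 37.5% |

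**5. Odds ratio against rate ratio.** The odds of any visit are (1 + k·m)^(1/k) − 1. At k = 1.0 this equals m, so the odds ratio equals the rate ratio. At k = 0.5 and a rate ratio of 1.40 per SD (comparing +0.5 with −0.5 SD), the odds ratio is 1.41 to 1.44 for a 2-month window and 1.43 to 1.50 for the 6-month window, depending on r. Whether the odds ratio can be read as a rate ratio therefore depends on a dispersion nobody knows yet.

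**6. Power at a rate ratio of 1.4 per SD, n = 100.** These come from 6,000 null and 6,000 alternative gamma-Poisson data sets per scenario, with exchangeable GEE, Mancl-DeRouen standard errors, and interval indicators in the binary model. Each test's critical value was set from its own null sets to give 5%. The last column repeats the comparison with a discrete 0–10 score having the plan's mean of 3.7 and SD of 2.7 (3,000 sets).

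| Visits/year | k | Count GEE | Any visit per interval | Loss, normal score | Loss, ACE-like score |
|---|---|---|---|---|---|
| 0.5 | 0.5 | 50.7% | 46.0% | 4.7 | 7.6 |
| 0.5 | 1.0 | 42.2% | 40.2% | 2.0 | 4.9 |
| 1 | 0.5 | 73.1% | 66.4% | 6.7 | 6.2 |
| 1 | 1.0 | 58.7% | 51.9% | 6.8 | 6.8 |
| 2 | 0.5 | 86.8% | 77.9% | 8.9 | 7.1 |
| 2 | 1.0 | 68.8% | 60.8% | 8.0 | 10.5 |

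Losses are in percentage points, with Monte Carlo standard error 0.8 to 1.4 (normal) and 1.1 to 1.7 (ACE-like).

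**7. Power at a rate ratio of 2.0 per SD.** Both analyses reach 93 to 100%, and the loss is about 1 point or less. One run of 1,000 sets per scenario gave 0.1 to 1.6 points; a power near 93% there has a standard error of √(0.93 × 0.07/1000) = 0.8 points.

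**The case against.** The strongest reply is that this is an omission, not a demonstrated error. The odds-ratio sentence follows directly on the one about the primary outcomes, which does not name ER visits, so it may be meant only for the yes/no outcomes. GEE fits counts perfectly well. The Sample size wording says the key outcomes include binary measures, not that all are binary. All of this stands: a reader might infer that the plan commits to dichotomising ER visits, and the documents do not say so. But on this reading the count has no stated effect measure at all, and the gap remains.

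A reader might also infer that no counting period is given. That is too strong: the first year of life and the assessment times are stated. Taken literally, the word postnatally in item 4 even suggests a running total since birth, from which interval counts follow by subtraction. Only the rule for each assessment is missing.

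A third tempting reading is a large power loss. A single yes/no split over 12 months would cost 9 to 41 points under the assumptions of step 6, but the plan specifies repeated measures, so that split is not its analysis. The loss that is relevant depends on the rate ratio assumed, and it nearly vanishes at 2.0. A rate ratio of 2 is not the same as the plan's odds ratio of 2, but it is a comparable effect.

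Finally, unequal intervals do not by themselves bias the ACE association, because all infants share the schedule. An exposure term matters where an interval is only partly observed.

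**Conclusion.** The point holds as a mismatch between hypothesis, data and effect measure, together with a missing counting rule for each assessment. An any-visit odds ratio would show the direction of the ACE or 7C association but would not estimate how much more frequent visits are.

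Its size, under 0.5 to 2 visits a year and dispersion 0.5 to 1.0: a split in each interval leaves 11 to 38% of visits out. With n = 100 and tests held at 5%, it loses roughly 2 to 10 power points at a rate ratio of 1.4 per SD and about 1 point or less at 2.0. Rate, dispersion and rate ratio are all assumptions. The documents do not support a claim that the study is underpowered for ER visits, or that the investigators have chosen to dichotomise. The change is worth making before data collection because it is cheap and the counting rule is hard to recover later; the binary outcomes are unaffected.

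**What to change.** At each of 2, 4, 6 and 12 months, record new ER visits since the last assessment and the months of infant time observed in that interval. Analyse these counts with a log-link GEE, robust standard errors and log(months observed) as offset. Report rate ratios per SD of ACE and of 7C with 95% confidence intervals, and keep odds ratios for the yes/no outcomes. If the investigators prefer a single effect measure, a less informative fallback is to pre-specify any new visit per interval, with interval indicators, and say that it does not estimate frequency.

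The cost is one sentence in the analysis plan, one added data field, and a different link and variance option in the same GEE software. The report gains a second effect measure. The count test may be slightly liberal at n = 100: null rejection at the nominal level was 5.0 to 6.8% in the simulations, even with a small-sample correction, which is optional. The offset handles partly observed intervals but does not correct for informative dropout.

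### The planned analysis does not match two parts of the hypothesis: ER visits are a count but the only stated effect measure is an odds ratio, and no ACE × 7C term addresses whether resilience counters ACE

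*Combined protocol and SAP*

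**What the plan says.** Section 2 (Hypothesis) looks at the baby's first year and predicts that mothers with substance use disorder who score higher on ACE "will have children with poor outcomes, including difficulty reaching developmental milestones, poorer adherence to vaccination schedule guidelines, and more frequent ER visits". It adds that "high maternal resilience scores may counter the high ACE scores". Section 1 is wider and covers mother and baby: "We will evaluate whether or not the outcomes of maternal and baby health can be identified early through maternal screening tools".

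Section 5.B describes the ER measure as "the number of times the child was admitted to the emergency room". Item 4 of its five-item outcome list asks: "How many Emergency Room visits did the baby have postnatally". That list is headed "Outcome measures being followed at birth of baby, and at 2, 4, 6 and 12 months after birth" and marks no item as primary or secondary.

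The Data Analysis paragraph says: "The primary outcomes (parenting, custody, continued treatment, etc.) will be analyzed using generalized estimating equations (GEE) appropriate for repeated measures over time". The next sentence promises odds ratios with 95% confidence intervals for the relationships of ACE and 7C with the clinical outcomes. The Sample size paragraph gives the same three examples and the same *etc.*, describes the key outcomes as including binary measurements, and claims more than 90% power with 100 subjects for an odds ratio of 2 per SD of ACE at a response proportion of 0.50.

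**The concern.** Two of the study's own predictions lack an analysis that answers them.

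**ER visits.** The prediction is about frequency and the datum is a number. An odds ratio compares the odds of a binary event, so it needs a cut-point. None is given, and neither is a rate ratio or a count model. The analyst would have to choose a cut-point later. With an any-visit cut-point, a baby seen once and a baby seen many times would count the same.

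**Resilience.** To say that resilience counters high ACE scores is, on one natural reading, to say that the ACE association is weaker when resilience is high. Separate associations of ACE and of 7C with an outcome do not estimate that.

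**Primary set (secondary point).** The examples before *etc.* match items 1 and 2 of the outcome list. The hypothesised infant outcomes are items 3 to 5, and neither the Sample size nor the Data Analysis paragraph names them. A reader of the results could not be sure which of them were planned as primary.

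**Working it through.** **1. The plan's own power figure.** Inputs from the Sample size paragraph: n = 100, odds ratio 2 per SD of ACE, response proportion p = 0.50, visits at 2, 4, 6 and 12 months. Assumptions: two-sided alpha 0.05 (none is stated) and within-subject correlation between 1 (equivalent to one visit) and 0.5.

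Power = Φ(ln 2 × √(100·p(1−p)/D) − 1.96), with D = (1 + 3ρ)/4, so D = 1 at ρ = 1 and D = 0.625 at ρ = 0.5.

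- p = 0.5, D = 1: 0.693 × 5 − 1.96 = 1.506, power 93.4%.
- p = 0.5, D = 0.625: 0.693 × 5/0.791 − 1.96 = 2.42, power 99.2%.

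The claim of more than 90% reproduces. With the variance evaluated at odds ratio 2, the range is 84.6% to 96.5%. The claim covers one binary outcome, one score (ACE) and p = 0.50. By the simple formula, power is 79–94% at p = 0.2 and 55–75% at p = 0.1. It says nothing about a count, about 7C or about effect modification.

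**2. ER visits, text side by side.**

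| Where | ER visits appear as |
|---|---|
| Section 2 | more frequent visits |
| Section 5.B, methods | a number of times |
| Section 5.B, outcome item 4 | how many visits |
| Section 5.B, Data Analysis | covered only by an odds ratio for the clinical outcomes |

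GEE is not the obstacle, because it accommodates counts through a log link. What is missing is the link, the effect measure and the counting window. The window matters because the intervals between assessments are 2, 2, 2 and 6 months: the last is three times as long as the others, so equal visit rates give unequal expected counts. It is also unclear whether each report covers the time since the last assessment or all time since birth. Power for the count cannot be computed, because no visit rate or dispersion is given.

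**3. Resilience.** With both scores standardised, a model without a product term is logit(p) = b0 + b1·ACE + b2·7C. The ACE slope is b1 at every level of 7C. With b3·ACE·7C added, the slope becomes b1 + b3·7C.

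Illustration (assumed): b1 = ln 2 = 0.693, and +1 SD of 7C halves it, so b3 = −0.347 and the interaction odds ratio is exp(−0.347) = 0.707.

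- ACE odds ratio at +1 SD of 7C: exp(0.347) = 1.41.
- At the mean: 2.00.
- At −1 SD: exp(1.040) = 2.83.

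The planned output would give one ACE odds ratio near 2 for all three.

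Power for b3, with the same formula, 0.347 in place of ln 2, and the scores taken as uncorrelated:

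- p = 0.5: 0.347 × 5 − 1.96 = −0.23, power 41%; with D = 0.625, 59%.
- p = 0.1: 0.347 × 3 − 1.96 = −0.92, power 18%; with D = 0.625, 26%.

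Expected precision at p = 0.5: the standard error is 1/5 = 0.20 (D = 1) or 0.20 × 0.791 = 0.158 (D = 0.625). The 95% interval around 0.707 is then about 0.48 to 1.05, or 0.52 to 0.96.

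**The case against.** **The plan does state an effect measure.** A reader might infer that ER visits have none. That goes too far: odds ratios are promised for the clinical outcomes and no outcome is excluded. What stands is that this measure does not fit a count unless it is dichotomised, and no dichotomy is defined.

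**Resilience may be meant as an opposing association.** On that reading a 7C odds ratio pointing the other way would answer Section 2, and it is planned. This is fair. The gap exists under the effect-modification reading, which the wording equally permits, and the plan does not say which is meant.

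***Etc.* has a natural meaning.** The five-item list stands under the same heading and there is no secondary category, so *etc.* plausibly means items 3 to 5. A reader might infer that the infant outcomes were dropped or demoted; no text says so. Nor do the documents support calling the maternal outcomes misplaced, since Section 1 covers mother and baby and the list in Section 2 is introduced as non-exhaustive. Only the missing statement stands.

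**Multiplicity.** A reader might infer a false-positive risk of 1 − 0.95^5 = 23% over five outcomes, or 1 − 0.95^10 = 40% over five outcomes and two scores. Those figures assume alpha 0.05 and independent tests, and matter only if one nominal result is presented as the main finding. Section 4 says "This is a prospective observational study"; the plan reports intervals and states no alpha or decision rule. The figures therefore do not describe an error in the plan, although the text does not rule out such use.

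**Conclusion.** The concern holds for two mismatches between hypothesis and analysis. First, a frequency hypothesis about a count is covered only by an odds ratio. Its cost in precision cannot be quantified from the documents, but any dichotomy loses frequency information. Second, under the effect-modification reading, nothing planned estimates whether resilience weakens the ACE association. If +1 SD of 7C halves the ACE log odds ratio, the plan would report one odds ratio near 2 where the values at ±1 SD of 7C are 1.41 and 2.83. This rests on the assumed halving, odds ratio 2 at mean 7C, and uncorrelated standardised scores. The power of 41–59% at p = 0.5 and 18–26% at p = 0.1 also rests on alpha 0.05 and correlation from 1 to 0.5.

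The open *etc.* is a lesser matter of missing detail. A reader might also infer that the power claim is wrong. It is not: it reproduces by the simple formula, but for a narrower case than the set of outcomes it introduces. The point should be fixed before outcome data are analysed.

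**What to change.** 1. **ER visits.** Define the counting window. If visits are recorded since the previous assessment, use a log-link count GEE with robust standard errors and log interval length as offset. If the count is cumulative, analyse the 12-month total with log follow-up time as offset. Report a rate ratio per SD of ACE with a 95% CI. Keep logistic GEE and odds ratios for the binary outcomes.
2. **Resilience.** Fit ACE and 7C in the same model and add an ACE × 7C term. Report it with its 95% CI as an estimate, and say that the study is not powered to test it.
3. **Outcome list.** Replace *etc.* in both paragraphs with a closed list drawn from the five items. The investigators choose the primary or secondary status of each before outcome data are analysed. State either a multiplicity rule, or that intervals are unadjusted and no single nominal result is confirmatory.
4. **Power statement.** Say that the figure of more than 90% applies to one binary outcome related to ACE at a response proportion of 0.50, without adjustment.

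Cost: somewhat more analysis work and an interaction estimate that will be imprecise. No new data, visits or participants are needed.
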